2.1 Study Design

Type of design: Randomized Controlled Trial

This will be a randomized, blinded trial of two postoperative bandaging techniques: wet-to-dry dressings vs. petrolatum with non-stick bandaging (see **Table 1).** Primary outcomes will be tracked using the PWAT, PUSH tool, and Wound QOL Survey (described below). Screening will be performed during regularly scheduled clinic visits with the principal investigator. Informed consent will be signed by the subject. A physical exam will be performed to assure that HS lesions suitable for surgical deroofing are present. Once subjects are deemed appropriate for the study, on the day of surgery the surgical sites will be marked with a skin marker and documented by body location. The surgical deroofing or excision procedure will then be performed by the principal investigator.

Study Phases are as follows:

Phase 1 (Day 0): Screening and Enrollment – patient's surgical date

Phase 2 (Weeks 1–Wound closure): patient survey completion and wound monitoring

Phase 3: Data Analysis

On the day of enrollment (patient's surgical date), patient age, sex, race, smoking history, and immunomodulatory medication use will be recorded. Assessment of wound size will also be measured by the PI on the day of surgery. The surgical procedure will be completed as it normally wound if the patient were outside the study. After the PI leaves the room, the patient is randomized to their treatment group and given their wound bandaging supplies and detailed instructions regarding the study protocol.

Patients will be instructed to expect receipt of a virtual RedCap questionnaire via electronic mail 1week post operatively and 2-weeks postoperatively. Questionnaires will continue to be sent every 2 weeks until the wound has fully closed. Disposable rulers will be provided that will be placed beside the wound for scale and patients will be instructed how to measure their wounds. The photos will be depersonalized and examined by the PI. Objective wound assessment will be completed using two standardized assessment tools. Wound assessment will be completed with the validated photographic wound assessment (PWAT) tool and the photographs will also be used to score and track wounds using the validated pressure ulcer scale for healing (PUSH) tool.

If at any point patients develop a wound complication or wound like to have their wound examined or checked, they will be given contact information for the research fellow to schedule a follow-up visit.

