	 Characterize and compare the two bandaging regimens in terms of wound healing after surgical deroofing and excisional procedures using the validated PUSH tool

 Characterize and compare the 2 bandaging regimens in terms of pain with dressing changes, as measured by the NRS, after surgical deroofing procedures

Test Article(s)	NA
(If Applicable)	
Study Design	Interventional Study Model: Parallel Assignment
	 This study is a randomized, blinded trial of two postoperative bandaging techniques after HS surgery: wetto-dry dressings vs. petrolatum with non-stick bandaging. Patients will be followed for a minimum of 6 weeks postoperatively with surveys to be completed at home, including a wound photograph, at weeks 1, 2, 4, and 6 weeks postoperatively. If wounds have not healed by week 6, then final healing may be tracked up to 12 weeks to monitor for complications.
	Number of Arms: 2
	Masking: Triple (Care Provider, Investigator, Outcomes Assessor)
	 Following the surgical procedure, the principal investigator (PI) exits the exam room. The PI is not present for bandaging administration and training and thus is blinded to the wound dressing technique. The patient is not blinded as bandaging will be administered at home.
	Allocation: Randomized
	Enrollment: 74
Subject Population	Accepts Healthy Volunteers: No
key criteria for Inclusion	Inclusion Criteria:
and Exclusion:	 Male & females ≥ 16 years of age
	 Patient must have undergone a standard-of-care surgical procedure for HS with planned secondary intention healing of the wound.
	 Must be able to provide adequate informed consent for themselves
	 Must be capable of performing either of the recommended wound care regimens on their own or have someone available to consistently assist with wound care.
	Exclusion Criteria:
	 Patients with surgically closed wounds (sutures, staples)
	 Patients with preference for specific types of bandaging protocols
	 Patients that have not been able to tolerate either wet-to- dry or petrolatum and non-stick bandages in the past

Number Of Subjects	74
Study Duration	Each subject's participation will last at least 6 weeks. Official Dates: April 25 th , 2022 – October 30 th , 2023 (18 months)

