Study Phases Screening Study Treatment Follow-Up Efficacy Evaluations	Study Phases: Phase 1 (Day 0): Screening and Enrollment Phase 2 (Weeks 1–Wound closure): survey completion and wound monitoring Phase 3: Data Analysis Primary efficacy evaluation will be completed using the validated PUSH tool, NRS tool, and Wound QOL survey.
Safety Evaluations	Monitoring for signs of wound infection will be included on regularly scheduled patient surveys. If pain scores become worse following bandaging within one of the wound dressing groups during periodic data reviews, then we may need to stop the study early if this becomes significant. Subjects will have the ability to contact us with any concerns and should other unanticipated adverse events be reported we will track them and address any serious adverse events or trends.
Statistical And Analytic Plan	The general goal is to demonstrate non-inferiority between the two bandaging types. The PUSH tool is the primary endpoint utilized to power for non-inferiority between the two wound bandaging techniques. There is no a-priori rationale for any exact non- inferiority margin. Instead, it is estimated that the expected half- width of a 97.5% confidence interval (i.e., the lower extension of a one-sided, Bonferroni-adjusted 98.75% CI) will be 0.61 SDs. Put differently, there would be 80% power to establish that the non- stick dressing is not 0.84 SDs worse than the wet to dry dressing. Utilizing the sample size of 74 patients calculated using the non- inferiority analysis for the PUSH tool actually provides the study sample size necessary to reliably identify a meaningful difference between the other two primary endpoints, the NRS tool and Wound QOL survey. Primary outcome measures will be reported as means and full ranges.
DATA AND SAFETY Monitoring Plan	We will be compiling and monitoring data on responses on an ongoing basis and reviewing every 2-3 weeks. If one group is demonstrating significantly worse outcomes before the planned end of the enrollment period, we will end the study early and report the results available at that time. All patient data collected in this study will be stored within the secure research software RedCap. Data access will be restricted to the research fellow as the primary data input source. Downloaded

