1.4 Primary Objectives

Primary Outcome Measures:

- 1. Change in Wound QOL Survey Score Over Time
 - a. A validated Wound Quality of Life (QOL) Survey will be administered that focuses on patient-reported outcomes of level of wound pain, pain with dressing changes (application and removal), satisfaction with the bandaging, and ease of application of the bandaging, all

17 elements on a 0-4 scale. Total score ranges from 0 to 4 with higher scores indicating a worse outcome.

- Time Frame: Administered at 1, 2, 4 and 6 weeks post-surgery
- 2. Change in PUSH Score Over Time
 - a. The pressure ulcer scale for healing (PUSH) tool is a validated means of measuring wound healing over time, specifically wounds that heal via secondary intent, by taking into account things like wound size and wound exudate, among others. Scores range from 0-17 with higher scores indicating inferior wound healing.
 - Time Frame: Completed at 1, 2, 4 and 6 weeks post-surgery utilizing images submitted by patients
- 3. Change in Pain with Dressing Changes
 - a. The numeric rating scale (NRS) will be used, where patients will be asked to rate pain with dressing changes and general pain on a scale from 0-10 with higher scores indicating worse pain. This information will be collected in the patient survey that is sent post-operatively.
 - Time Frame: Collected at 1, 2, 4 and 6 weeks post-surgery

Secondary Objective

The PWAT will be an important secondary endpoint for evaluation and comparison with the primary endpoints. Other patient-reported outcomes including interference with daily activities/exercise, assistance needed with bandaging changes, bandage change difficulty, and likelihood to use this bandage type in the future will be assessed. Additionally, patient-reported wound healing will be recorded. This will include questions such as "To what degree is the wound healed?" with answers on a 10-point scale ranging from "completely healed, somewhat healed, not healed." Number of days to wound healing/resolution will be asked on all surveys 4 weeks and later. Patients will also be asked whether or not they believe their wound is showing signs of infection.

2 INVESTIGATIONAL PLAN (brief overview)

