8. DATA COLLECTION AND MANAGEMENT

All patient data collected in this study will be stored within the secure research software RedCap. Data access will be restricted to the research fellow as the primary data input source. Downloaded data will be secured on the UNC hospital cloud and only de-identified data will be sent via email. The principal investigator will not have access to any patient data until the de-identified data is provided for analysis at the conclusion of the study. Data will be coded according to established coding protocol.

Quality assurance is built into data collection process by ensuring that source data documents capture data in established/standardized format that aligns with establish coding standards.

Project manager will monitor data throughout the study to ensure all data is source verified. Data will be monitored after the first patient is enrolled, after the first 50% of patients are enrolled, and again at the end of the study (last patient, last follow-up). Regular meetings will be scheduled to ensure that data is cleaned along the way (not just at the end).

Data archiving: coded data will be stored on the Department share drive which is backed up and maintained by the school of medicine. Only study personnel will have access to the study data.

Data from patient surveys will all be collected at the same time so it is unlikely that we will be missing many data points. If patients fail to enter data at specific time points on their surveys we will use the previous value carried forward to the missing data point. The data for patients who do not return their surveys will not be included in the study analysis as it will be too difficult to correctly estimate their responses.

Data Safety Monitoring Plan

We will be compiling and monitoring data on responses on an ongoing basis and reviewing every 2-3 weeks. If one group is demonstrating significantly worse outcomes before the planned end of the enrollment period, we will end the study early and report the results available at that time.

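### The survey schedule contradicts itself on whether questionnaires stop at wound closure, and no rule says how a healed patient is scored up to week 6

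*Combined protocol and SAP*

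**What the plan says.** Two schedules stand side by side in the combined protocol and SAP.

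**Ends at closure.** Section 2.1 announces questionnaires at 1 and 2 weeks and then states: "Questionnaires will continue to be sent every 2 weeks until the wound has fully closed". The same section defines "Phase 2 (Weeks 1–Wound closure): patient survey completion and wound monitoring", and the Study Phases row of the synopsis agrees: "Phase 2 (Weeks 1–Wound closure): survey completion and wound monitoring".

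**Fixed to week 6.** The Study Design row of the synopsis sets the survey calendar: "surveys to be completed at home, including a wound photograph, at weeks 1, 2, 4, and 6 weeks postoperatively". That row attaches no healing condition to these four weeks, and the Study Duration row adds "Each subject's participation will last at least 6 weeks". Section 1.4 (Primary Objectives) gives weeks 1, 2, 4 and 6 for each of the three primary outcomes; for PUSH the entry is "Completed at 1, 2, 4 and 6 weeks post-surgery utilizing images submitted by patients". Section 3.3 lists the same four weeks and makes only later surveys conditional. Section 2.3 records outcomes for up to 6 weeks, which fits either schedule.

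**Missing data.** Section 8 carries the previous value forward where a patient fails to enter data at a time point. It also says: "The data for patients who do not return their surveys will not be included in the study analysis". Nothing addresses a survey withheld because the wound had closed.

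**The concern.** Taken literally, section 2.1 governs the week 4 and week 6 surveys, since two-weekly sending after week 2 falls on exactly those weeks and no other sentence in that section sends them. All three primary outcomes come from the surveys and their photographs, so stopping at closure would stop the primary data for the patients with the best healing. Whether a patient has a week-6 score would then depend on healing, which is what PUSH measures, and the arms would be compared on subsets selected after randomisation.

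The plan expects healing within this window: section 1.4 (Primary Objectives) asks for days to healing from week 4 onward, and the synopsis treats a wound still open at week 6 as the special case. The documents do not say who declares closure. Under sections 4 and 8 the principal investigator scores wounds at the end of the study and has no patient data before then, so the trigger would most likely be the report of the patient, who is not blinded.

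**Working it through.** **1. The plan's own PUSH figures.** Statistical Considerations gives 28 per arm (from the pain calculation), a half-width of 0.61 SD for a 97.5% interval (one-sided level 0.0125), and 80% power to exclude 0.84 SD.

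- Half-width = t(0.9875, 2n−2) × √(2/n). With n = 28: 2.306 × 0.2673 = 0.616 SD (0.599 with a normal quantile). The stated value is 0.61.
- Power, for a true difference of 0, comes from the noncentral t with noncentrality 0.84 × √(n/2) = 0.84 × √14 = 3.143 on 54 degrees of freedom. The result is 79.6%. The stated value is 80%.

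So the stated figures correspond to about 28 scored patients per arm at the analysed visit.

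**2. Precision if healed patients have no week-6 score.** The share healed is assumed, because the documents give none. The plan also names no week for the PUSH comparison; week 6 is taken here. The same formulas apply with n = 28 × (1 − share), rounded.

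| Assumed share per arm without a week-6 score | n per arm | Half-width (SD) | Power at 0.84 SD |
|---|---|---|---|
| 0% | 28 | 0.62 | 80% |
| 10% | 25 | 0.65 | 74% |
| 20% | 22 | 0.70 | 68% |
| 30% | 20 | 0.74 | 63% |
| 50% | 14 | 0.90 | 45% |

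**3. Effect of selection on the difference.** Illustrative model, all inputs assumed: a latent score X is normal with SD 3, PUSH = max(0, X), and a wound is healed when X ≤ 0. For healed share h, put a = −z(h), where z(h) is the normal quantile. The mean over all patients is 3 × [a(1 − h) + φ(a)]; the mean over open wounds is that value divided by (1 − h).

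- Wet-to-dry, h = 0.45: a = 0.1257, φ(a) = 0.3958; all patients 1.395, open wounds 2.536.
- Non-stick, h = 0.30: a = 0.5244, φ(a) = 0.3477; all patients 2.144, open wounds 3.063.
- Non-stick minus wet-to-dry: 2.144 − 1.395 = 0.75 in all patients; 3.063 − 2.536 = 0.53 in open wounds. Shrinkage is 1 − 0.53/0.75, about 30%.
- With the arms swapped (non-stick better) the differences are −0.75 and −0.53. With equal healing in both arms, both differences are 0.

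**4. Which visits are exposed.** Section 2.1 sends the week 1 and week 2 surveys to everyone. Under the closure rule, week 4 would lose those who reported closure by week 2, and week 6 would lose those who reported it by week 4. The pain calculation (1.3 points, SD 1.4) is set at week 2, so it is little affected.

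**The case against.** The strongest reply is that this is loose wording in a section labelled a brief overview. The synopsis, section 1.4 (Primary Objectives) and section 3.3 all fix four surveys; section 3.3 makes only later ones conditional; and asking days to healing on surveys from week 4 presupposes that healed patients answer them. The sentence in section 2.1 could be meant for the period after week 6. This stands to the extent that a reader who infers that healed patients will certainly have no later primary scores goes further than the documents allow. It does not remove the contradiction, because the study phases also end at closure and section 2.1 has no other provision for weeks 4 and 6.

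Second, the survey that reports closure would usually carry a photograph of the closed wound, so a carried-forward PUSH would often be the healed score. That is fair for PUSH, provided carry-forward applies at all. Section 8 speaks of data not entered and surveys not returned, and a survey never sent is not clearly either. If closure became known by an unscheduled contact, the last value could pre-date it.

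Third, a reader might infer a bias towards non-inferiority. That direction holds only if non-stick is truly worse; if it is better, the shrinkage hides benefit. The loss of patients also widens the interval, which makes non-inferiority harder to show. Nor need the difference vanish among open wounds: that would require equal mean scores in the unhealed wounds of both arms, which nothing in the documents supports.

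Finally, a wound that re-opens need not go unnoticed, since patients may contact the clinic or the research fellow, or book a visit, at any time.

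**Conclusion.** The point holds as an unresolved contradiction with a missing scoring rule. It is not established that the trial will lose its healed patients. If the closure rule is the one applied, the week 4 and week 6 comparisons could be confined to unhealed wounds, with a true difference shrunk in either direction and precision reduced. Under an assumed 20% per arm without a week-6 score, power at 0.84 SD falls from about 80% to about 68%; the roughly 30% shrinkage rests wholly on the assumed latent-normal model and healing shares. The actual size cannot be derived, because no healing rate is given. If all four surveys go to everyone and are returned as planned, the stated power is unaffected, though post-closure scoring would still be undefined.

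**What to change.** Reconcile section 2.1 and the Study Phases text with the synopsis schedule, section 1.4 (Primary Objectives) and section 3.3:

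- Send the week 1, 2, 4 and 6 surveys, with photograph, to every randomised patient whatever the healing status. Make only surveys after week 6 conditional on an open wound.
- Where the last returned survey and photograph show closure and no later photograph arrives, score PUSH as 0, the bottom of its 0–17 scale, at the remaining visits up to week 6. Do not exclude the patient or carry forward a pre-closure value.
- State how Wound QOL and dressing-change NRS are handled once dressings have stopped.
- Report the number healed by arm and visit.

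The cost is a wording change, an adjusted survey schedule, and one or two extra short surveys (weeks 4 and 6) for healed patients. Section 2.3 already records an actual enrolment of 74. If follow-up is over, the sponsor can still state which schedule was run, apply the PUSH rule and report the healed counts.

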2.2 Allocation to Treatment Groups and Blinding

Following the surgical procedure, the principal investigator ([name]) will exit the exam room. The principal investigator will thus be blinded to the wound dressing technique as he will not be present for bandaging administration, but the patient will not be blinded as they themselves will be administering the bandaging at home. The research fellow will complete randomization via the RedCap randomization algorithm and inform the patient of their assigned group.

2.3 Study Duration, Enrollment and Number of Subjects

Duration: primary and secondary outcome data will be recorded for up to 6 weeks, and if wounds are not healed by week 6, then subjects may be followed out to 12 weeks for safety.

Planned enrollment: minimum 72, maximum 100. Actual: 74

2.4 Study Population

Accepts Healthy Volunteers: No

Inclusion Criteria:

- Male & females ≥ 16 years of age
- Patient must have undergone a standard-of-care surgical procedure for HS with planned secondary intention healing of the wound.
- Must be able to provide adequate informed consent for themselves

- Must be capable of performing either of the recommended wound care regimens on their own or have someone available to consistently assist with wound care.

Exclusion Criteria:

- Patients with surgically closed wounds (sutures, staples)
- Patients with preference for specific types of bandaging protocols
- Patients that have not been able to tolerate either wet-to-dry or petrolatum and non-stick bandages in the past

3 STUDY PROCEDURES (what will be done)

3.1 Screening/Baseline Visit procedures

Subjects with a diagnosis of hidradenitis suppurativa will be identified in a subspecialty clinic dedicated to hidradenitis suppurativa in the UNC Dermatology Clinic. Subjects will be selected for potential enrollment on the day of surgery. The research fellow will approach the patient and inform them of their eligibility and describe study details. If patient agrees, informed consent will be obtained and enrollment initiated. Baseline demographics will be obtained, including medical history, BMI, age, sex, race, etc.

3.2 Intervention/Treatment procedures (by visits)

After study enrollment, patient will undergo their previously-scheduled surgery. The PI will exit the room, and the patient will be randomized to their treatment group. Bandaging of their wound will be completed, bandaging supplies will be given, and detailed follow-up instructions will be provided.

3.3 Follow- up procedures (by visits)

Patients will have no scheduled follow-up visits in person. They will instead receive surveys at weeks 1, 2, 4, 6, and after if necessary. However, patients may schedule an in-person visit at any time.

3.4 Unscheduled visits

Patients may schedule an in-person visit at any time if they have concerns regarding wound healing or general questions regarding the process. They are encouraged to contact the research fellow for research study specific questions.

3.5 Subject Completion/ Withdrawal procedures

If at any point the patient desires to withdraw from the study, he/she may do so for any reason.

3.6 Screen failure procedures

If a patient does not meet inclusion criteria at enrollment, normal clinical care will resume with no detriment to the patient.

4 STUDY EVALUATIONS AND MEASUREMENTS (how measurements will be made)

- List variables that will be abstracted from medical charts

Page **12** of **20**

Baseline demographics including age, sex, race, BMI, smoking history, among others will be recorded from the medical chart and verified with the patient on the day of enrollment.

- Describe baseline evaluation

Baseline evaluation will include identifying surgical site, evaluating if surgical site is optimal for study inclusion, assessment of patient's overall general health,

- Describe how measurements will be taken.

Patient's upload a photo of their wound with each online survey they complete, as well answers to questions such as pain with wound dressing changes on a scale 1-10. Wound measurements and wound characterization for the primary and secondary endpoints will then be completed at the conclusion of the study by the PI. Other questions and data will be inputted by patients directly on the survey for future statistical evaluation.

- Describe rating scales, tests, psychological tools, laboratory evaluations, etc.

The previously-described PUSH, Wound QOL, and NRS primary endpoints will all be recorded and extrapolated from the online surveys submitted by patients at scheduled intervals.

STATISTICAL CONSIDERATIONS

Our study is powered to detect an effect on our primary endpoints, pain and quality of life. Although we will use the Wound Quality of Life (QoL) survey for our main analysis, as it is more comprehensive and we think readers will find it more persuasive, we don't have direct data on what to expect. Rather, we do have a strong sense, from clinical experience, of what will happen with pain. Using the 0-10 numerical pain scale, we believe the non-stick dressing will reduce pain ratings by 1.3 points at the two-week checkup and estimate the historical SD at that visit is 1.4 units, implying a .93 SD reduction. We calculate we will need 28 patients per arm to achieve 80% power. We add 2 more to account for two planned covariates (pelvic area vs armpit, and initial wound size). Since we expect approximately 20% dropout, we will plan to recruit approximately 74 patients.

There are approximately 6-8 new patients per week, and we conservatively estimate at least 2 will consent to the study. Thus, we should be able to reach our desired sample size in 36 weeks. With 6 weeks of required follow-up, the last patients should be finished by 42 weeks, well within 1 year. If our recruitment and/or retention is better, we will continue to gather data, again yielding better power. Our other primary endpoint is efficacy. We believe the non-stick dressing will not lead to reduced wound healing compared to the traditional wet to dry dressing. We don't have an a-priori rationale for any exact non-inferiority margin. Instead, we estimate that the expected half-width of a 97.5% confidence interval (i.e., the lower extension of a one-sided, Bonferroni-adjusted 98.75% CI) will be 0.61 SDs. Put differently, we would have 80% power to establish that the non-stick dressing is not 0.84 SDs worse than the wet to dry dressing.

Aim 1. Characterize and compare the 2 bandaging regimens in terms of pain with dressing changes after a surgical deroofing procedure

Hypothesis for Aim 1: Rating of pain will be less in the petrolatum and non-stick bandaging group compared to the wet-to-dry group

We are using the numerical rating scale (NRS) for pain that ranges from 0-10. From prior studies on the NRS, we know that the minimal clinically significant difference in pain on the scale is approximately 1.3 points [6]. We believe the non-stick dressing will reduce pain ratings by 1.3 points at the two-week checkup and estimate the historical standard deviation between patients pain ratings at that visit is 1.4 units, implying a .93 SD reduction. Our ability to detect this difference and achieve 80% power is far exceeded by the 74 patients needed to detect non-inferiority via the PUSH tool (see Aim 3). We will report means and full ranges for NRS values in each group across relevant time points.

Aim 2. Characterize and compare the 2 regimens via patient-centered outcomes outlined in the validated Wound QOL Survey and additional questions

Hypotheses for Aim 2: Patient QOL ratings will be more favorable in the petrolatum and non-stick bandaging group compared to the wet-to-dry group

The minimal important difference (MID) in Wound-QoL-17 overall score was determined in a German sample of 227 patients with chronic wounds and was found to be approximately 0.5 [4]. This means that a decrease of the Wound-QoL-17 total score of 0.50 or more in a group of patients can be assumed to indicate patient-relevant change. The global score ranges from 0 (= no impairment) to 4 (= maximum impairment). Preliminary statistical analysis indicated that we would need only 3 patients in each study arm to detect this difference. As a result, the study sample size necessary to meet this number to achieve 80% power is far exceeded by the 74 patients needed to detect non-inferiority via the PUSH tool (see Aim 3). We will report means and full ranges for Wound-QOL values in each group across relevant time points.

Aim 3. Characterize and compare the two bandaging regimens in terms of wound healing after surgical deroofing and excisional procedures using the validated PUSH and PWAT tools

Hypotheses for Aim 3: Wound healing in the petrolatum and non-stick bandaging group will be noninferior compared to the wet-to-dry group

The pressure ulcer scale for healing (PUSH) tool is a well-validated and accurate measure of healing for chronic wounds that heal by secondary intention. However, it has not been used frequently by the principal investigator as a measure of wound healing. Given our unfamiliarity in the clinical variance of PUSH scores between patients, we plan to power for non-inferiority between the two wound bandaging techniques in terms of wound healing as opposed to superiority of one bandaging type over the other. We don't have an a-priori rationale for any exact non-inferiority margin. Instead, we estimate that the expected half-width of a 97.5% confidence interval (i.e., the lower extension of a one-sided, Bonferroniadjusted 98.75% CI) will be 0.61 SDs. Put differently, we would have 80% power to establish that the non-stick dressing is not 0.84 SDs worse than the wet to dry dressing.

The photographic wound assessment tool (PWAT) is not a primary endpoint for which the study is powered, but it will still be completed and analyzed as a secondary outcome of interest and reported as means and full ranges.

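### The 3 patients per arm said to suffice for a 0.5-point Wound-QoL difference has no documented basis and requires a very small SD, so the claim of ample power on this primary endpoint is unsupported

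*Combined protocol and SAP*

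**What the plan says.** Statistical Considerations, Aim 2 takes a minimal important difference (MID) of 0.5 on the 0-4 Wound-QoL-17 global score. It words the MID as a change within a group: "a decrease of the Wound-QoL-17 total score of 0.50 or more in a group of patients can be assumed to indicate patient-relevant change". It then states: "Preliminary statistical analysis indicated that we would need only 3 patients in each study arm to detect this difference", and concludes that "the study sample size necessary to meet this number to achieve 80% power is far exceeded by the 74 patients" said to be required for PUSH non-inferiority. The synopsis (Statistical And Analytic Plan) repeats the assurance for pain and Wound-QoL together, saying that 74 provides "the study sample size necessary to reliably identify a meaningful difference between the other two primary endpoints".

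The opening of Statistical Considerations names Wound-QoL for the main analysis but says of it that "we don't have direct data on what to expect". For pain, the same section gives an effect (1.3 points), an SD (1.4) and a visit (two weeks). No such inputs appear for Wound-QoL. For reporting, Aim 2 commits only to means and full ranges by group.

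**The concern.** A sample size for a difference in means needs an SD, an alpha and a test. Aim 2 gives an exact number with none of these, for a survey on which the plan says it lacks direct data. Three per arm is also very small for a shift of one eighth of the scale (0.5 of 4).

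A reader is told that power on Wound-QoL is not in question. If the SD is larger than the figure implies, a null result could be taken as well-powered evidence of no difference. Means and full ranges would not correct that, because they do not show whether a difference of 0.5 points has been excluded.

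**Working it through.** **Inputs from the documents.** Difference 0.5 points, 3 per arm, power 80% (Aim 2). 74 recruited, about 20% dropout, two planned covariates (opening of Statistical Considerations). Not given for Wound-QoL: SD, alpha, sidedness, test, visit.

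**Step 1. Do the plan's other figures reproduce?** Yes.
- Pain: "We calculate we will need 28 patients per arm to achieve 80% power". With d = 1.3/1.4 = 0.93, a two-sample t-test needs 20, 24 or 28 per arm at two-sided 0.05, 0.025 or 0.0125. The stated 28 matches the last, although the plan gives no alpha for pain.
- PUSH: "we would have 80% power to establish that the non-stick dressing is not 0.84 SDs worse than the wet to dry dressing". At 28 per arm (54 df) and one-sided 0.0125, the half-width is 2.306 × √(2/28) = 0.616 SD (plan 0.61), and the margin with 80% power is 0.844 SD (plan 0.84).

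The Wound-QoL figure cannot be reproduced forwards, so I solved for the SD it requires.

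**Step 2. Largest SD at which 3 per arm gives 80% power for 0.5 points.** Normal approximation: d = (z for alpha + z for power) × √(2/n). At one-sided 0.05 this is (1.645 + 0.842) × √(2/3) = 2.03, so SD = 0.5/2.03 = 0.246. The t-test values come from the noncentral t distribution with 4 df.

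| Between-arm method | Required d | Largest SD |
|---|---|---|
| t-test, two-sided 0.05 | 3.07 | 0.163 |
| t-test, two-sided 0.025 | 3.74 | 0.134 |
| t-test, two-sided 0.0125 | 4.52 | 0.111 |
| Normal approximation, two-sided 0.05 | 2.29 | 0.219 |
| Normal approximation, one-sided 0.05 | 2.03 | 0.246 |

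The between-arm ceiling is therefore 0.11 to 0.25, which means a difference of 2.0 to 4.5 SD. The plan's own pain effect is 0.93 SD. On a within-arm reading, the most lenient case (normal approximation, one-sided 0.05) gives d = 2.487/√3 = 1.436 and SD = 0.348. The one-sample t-test at two-sided 0.05 gives 0.153.

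These ceilings apply to the SD of whatever is analysed, which is the residual SD if the analysis is adjusted.

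**Step 3. What the enrolled sample supports.** 74 × 0.8 = 59.2, about 30 evaluable per arm. The plan says "We add 2 more to account for two planned covariates"; taking 2 off per arm leaves an effective 28. The difference detectable with 80% power is then:
- two-sided 0.05: 0.762 SD, so 0.5 points needs SD ≤ 0.5/0.762 = 0.656
- two-sided 0.025: 0.844 SD, so 0.5 points needs SD ≤ 0.5/0.844 = 0.593

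**Step 4. Sensitivity to the SD.** All SDs here are assumptions. 0.56 is the pain SD rescaled (1.4/10 × 4), which borrows from a different instrument. 0.8 and 1.0 have no anchor in the documents and only show the direction.

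| Assumed residual SD | Power at 28 per arm, 0.05 / 0.025 | n per arm for 80%, 0.05 / 0.025 |
|---|---|---|
| 0.50 | 96% / 92% | 17 / 21 |
| 0.56 | 91% / 85% | 21 / 26 |
| 0.60 | 87% / 79% | 24 / 29 |
| 0.80 | 63% / 52% | 42 / 50 |
| 1.00 | 45% / 34% | 64 / 78 |

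At SD 0.56, 3 per arm would have 13% power (0.05) or 7% (0.025).

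**Step 5. What an interval would show.** At 28 per arm the 95% half-width is 2.005 × √(2/28) = 0.536 SD. With an observed difference of zero, the interval excludes 0.5 points if the SD is below 0.5/0.536 = 0.93. For a 97.5% interval the limit is 0.5/0.616 = 0.81.

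**The case against.** Several points on the other side stand.

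- **The synopsis sentence covers pain too.** For pain the plan states effect, SD and visit, and about 30 evaluable per arm gives 80% power even at two-sided 0.0125. Only the Wound-QoL half of that sentence is unsupported.
- **The ceilings are not limits on any raw SD.** The plan collects the survey at four visits. If the analysed quantity were a four-visit mean, with an assumed between-visit correlation of 0.3 to 0.7, the lenient ceiling of 0.246 would correspond to a raw single-visit SD of about 0.36 to 0.28. That is still small, and the plan does not say such a mean was used.
- **Adjustment could help.** Section 6 (Randomization procedures) says wound size and location can matter considerably for the survey and should be controlled for. If they explained an assumed 30% of the variance, power at raw SD 0.56 and 28 per arm would be about 98% (0.05) or 95% (0.025). The same remark suggests that unadjusted scores are not tightly clustered, so it cuts both ways.
- **Lack of direct data need not mean that no SD existed.** In context the phrase contrasts Wound-QoL with the expected effect on pain. A preliminary analysis may have had an SD that is not reported. The supportable statement is that it is not documented here.

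A reader might go further and infer that the 3 is an arithmetic error, or that the trial is too small for Wound-QoL. The documents support neither. Without the inputs the figure cannot be shown to be miscalculated, and 28 per arm is enough at every residual SD up to about 0.59 to 0.66, which the documents neither confirm nor exclude. Nor did the 3 set the sample size: the plan attributes 74 to pain in one place and to PUSH in others.

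**Conclusion.** The point holds as an undocumented power claim on a primary endpoint. It is minor. The figure of 3 per arm needs a residual SD of at most about 0.11 to 0.25 between arms, or 0.35 on the most lenient within-arm reading, and no passage gives an SD of any size. The conclusion that 74 far exceeds the need is therefore unsupported for Wound-QoL.

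This rests on a 0.5-point target and 80% power, both stated in the plan, and on standard tests and alphas, which I had to assume. The between-arm reading is the natural one, because Aim 2 hypothesises better ratings in one arm than in the other. Section 2.3 already gives actual enrolment as 74, so no design decision changes. What changes is how the power is described and how the Wound-QoL result can be read.

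**What to change.** 1. In Aim 2, delete the 3 per arm and the statement that 74 far exceeds the need. Alternatively, give the SD with its source, and the test, alpha and visit actually used. If none can be given, write: No SD was available for this survey. With about 30 evaluable patients per arm (effective 28 after the covariate allowance) there is 80% power for a between-arm difference of 0.76 SD at two-sided 0.05 or 0.84 SD at 0.025. For 0.5 points this requires a residual SD of about 0.66 or 0.59 or less. Keep the alpha that applies and say which it is; 0.025 matches the PUSH figures.
2. In the synopsis, soften the assurance for Wound-QoL only and leave pain as it is.
3. In addition to means and full ranges, report the between-arm Wound-QoL difference at a named visit, adjusted for location and initial wound size, with a confidence interval at the matching level read against 0.5 points. State that the MID is worded as a within-group decrease and is used here as a between-arm benchmark.
4. Label as post hoc any visit, alpha or model chosen after data were seen. The document is dated 8/1/2024, after the stated study end of October 2023.

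Cost: wording, one interval and a less favourable stated power. No extra patients.
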